During this study we will: 1) Conduct a pilot test with WWIDs (n=68) randomized to either a “Basic” or “Enhanced” intervention. Women randomized to the “Basic” group will receive general PrEP counseling from the study physician and PrEP counselor at Prevention Point, general written materials, as well as “general” reminder text messages for appointments. Those in the “Enhanced” group will receive targeted counseling by a trained PrEP counselor who will emphasize the targeted messages, doctor counseling, customized written materials, as well as supportive targeted text messages and reminders. Targeted messages and materials are informed by our formative findings. Both groups will get assistance with making their doctor appointments and will have PrEP dispensed at Prevention Point’s medical clinic. 2) To assess promise of efficacy, we will compare PrEP adherence (biomedical testing, self-report) as primary outcomes at one month, end, and three-month follow-up. We will compare changes to self-efficacy, decisional conflict, and PrEP perceptions as secondary outcomes. To assess feasibility and acceptability we will compare attitudes about the intervention, prescription pick up, and number of text messages opened. Figure 1 illustrates the study design:

Figure 1. RCT Study Design

**HIV- WWIDS
(n=68)(randomized)**

“Basic” Group

- General PrEP counseling by study physician and PrEP counselors at PPP
- General written materials on PrEP
- Assistance with medical appointments
- Prescription pick-up at PPP
- General text message reminders of appointments

“Enhanced” Group

- General PrEP counseling by study physician and targeted PrEP counseling by trained counselor
- Targeted materials based on formative findings
- Assistance with medical appointments
- Prescription pick-up at PPP
- Targeted supportive text messages and reminders

Randomized Pilot

We will recruit and enroll 68 WWIDs from syringe exchange who consent to participate in the intervention and will be randomly assigned to either the “Enhanced” or “Basic” group. Both groups will participate for six months (three months in the intervention and a three month follow-up), receiving PrEP counseling at Prevention Point (intervention monthly; control as requested by the participant), educational materials (targeted vs. general) and PrEP reminders via text messages (intervention also receives supportive messages about PrEP use). They will

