Worry that taking medication will interfere with drug use.	I know you might worry that taking PrEP might interfere with your daily life, especially if you are	There is no evidence that taking PrEP will interfere with taking other substances.	Getting your medication is easy and doesn't interfere with other use.

	using substances. But there is no reason to worry. PrEP is safe and easy to take and because you are getting it here at Prevention Point, it is easy to talk.		Call XXX_XXX_XXX if you have ?s!
Don't believe doctors will want to treat WWIDs or care about them staying HIV-	I know sometimes it's hard to go to the doctor, but we have doctors who really care about our clients and who want you to stay HIV negative.	Some people do not like to go to the doctor, but using PrEP can help you stay HIV-. We only send our clients to doctors we know will work with you and who care about your health.	Remember...UR doc wants you to keep taking your medication every day! Call XXX-XXX-XXXX if you have ??

All participants will receive study text messages throughout the study. “Enhanced” group participants will receive weekly text messages. These texts will include supportive messages about taking PrEP that emphasize why they should continue to take their PrEP as prescribed, as well as reminders to pick up their medication. “Basic” group participants will receive bi-monthly text message reminders to pick up their medication. We will work with Mosio, which provides text messaging services and has experience working with studies funded by the National Institutes of Health. Temple University has signed a contract with Mosio for this service. In that contract is a data sharing agreement that states that any data collected for the study will be shared with [name], the Principal Investigator, and cannot be used for any other purpose.

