Mosio will have no identifying information other than a participant’s phone number. Mosio will collect user data on the number of participants who open the text messages and will also resend text messages if they remain unopened for more than two days to assess feasibility. In addition, participants will be provided the opportunity to engage with study personnel if they have questions. A phone number will be provided in every text and study personnel will be available to take participant’s phone calls and answer their text messages. All messages/calls are sent to the study coordinator’s email and we will provide language that indicates that if questions are after business hours of 9 am to 5 pm we will answer the question the next morning. There will also be an opportunity to provide feedback. At mid-intervention participants will be asked to text back an answer to an adherence question. This provides an opportunity for participants to be actively engaged and to assess feasibility and acceptability. We will receive weekly reports from Mosio on which participants have opened text messages to assess feasibility.

At the end of the first month, all participants will also receive a text asking about their adherence to PrEP. They will respond with a 1 or 0 to indicate they have or have not taken PrEP the previous day. To help alleviate any problems with running out of cell phone minutes, every participant will receive a \$25 gift card to help pay for minutes needed. If they lose or have their cell phone stolen, we will assist them in getting a new one through the current services at PPP.

PPP has a current service that provided assistance to clients and we will work with them to help the study participant.

At the end of the first month we will also contact participants about completing a quick assessment of adherence and acceptability of the intervention. This will be done in person at Prevention Point. Similarly, at the end of the three-month intervention study staff will contact participants about completing a post-test assessment. We will attempt to correspond assessments to be at a time when they are already at Prevention Point and ideally meeting with their PrEP counselor or there for other services.

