Participants will also continue to be monitored by the physician at Prevention Point. It is expected that a blood test or urine sample measuring PrEP levels and an HIV screening test would be done at the beginning, mid-point and the end of the intervention. It will also be done three months after the intervention is over. This will provide biomedical adherence data and ensure that participants have remained HIV negative.

After the intervention is over, all study participants may continue their PrEP prescription and have it administered out of the medical clinic at Prevention Point. In addition, PrEP counselors will remain available for participants should they have any further questions. Specialized counseling and text messages will no longer be provided. Three months after the intervention is over, we will contact participants to complete the last study assessment. This will be done at Prevention Point when the participant is there.

Instruments

There are five study assessments (See attachments). They include:

1. Eligibility Screener
2. Baseline Assessment
3. Mid-Intervention Assessment (in person and one question via text)
4. Post-Intervention Assessment
5. Three month follow-up Assessment

Analysis Plan

General - All data will be graphed and tabulated by treatment group for review of distributional properties and anomalous values prior to the main analyses. Continuous and normally distributed variables will be summarized with means and standard deviations. All parameter estimates will be bound by 95% confidence intervals and tests for differences in means and proportions will be deemed statistically significant $p < 0.05$. Post-hoc tests of significance will be based on adjustments for alpha to protect family-wise error rates at 5% using the method of Benjamini & Hochberg. For all analyses described in this study, we will use Statistical Analysis Software (SAS, version 9.4, Cary, N.C.).

Primary Outcome. The study's intent is to provide directional insight into the design of subsequent programmatic studies. As such, univariate group comparisons will be accomplished using an independent two-sample t-test for continuous measures (or non-parametric Wilcoxon

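### Feasibility is compared on the number of texts opened, but the arms are sent different numbers of texts, so identical opening behaviour gives Enhanced about twice the count

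*Combined protocol and SAP*

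**What the plan says.** The Study Design section of the protocol sets out how feasibility and acceptability will be judged: "we will compare attitudes about the intervention, prescription pick up, and number of text messages opened". The text measure is worded as a number, with no denominator.

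The text-message paragraphs of Procedure Phase 3 give the sending schedule. Enhanced "group participants will receive weekly text messages"; Basic "group participants will receive bi-monthly text message reminders to pick up their medication". The protocol does not say whether bi-monthly means twice a month or every two months. At the end of month one, "all participants will also receive a text asking about their adherence to PrEP". Participation is divided into "three months in the intervention and a three month follow-up", and after the intervention "Specialized counseling and text messages will no longer be provided".

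The same section describes the data in other terms: "Mosio will collect user data on the number of participants who open the text messages and will also resend text messages" that stay unopened for more than two days. It adds that weekly vendor reports will show which participants opened texts.

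The acceptability and feasibility paragraph, which is the same in the protocol's Analysis Plan and in the SAP, names two objective measures: opened texts and prescription pick-up. Each feasibility measure is to be looked at in both groups, descriptively and without a significance test. That paragraph does not define an opening rate either.

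**The concern.** A count of opens depends on how often a woman opens a text and on how many texts she is sent. The second factor is fixed by arm. A comparison of counts therefore mixes engagement with sending volume, and volume favours Enhanced by design.

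The study is a pilot whose stated purpose includes feasibility and acceptability. If the count is tabulated as worded, a higher figure in Enhanced could be taken as better engagement with the targeted messages when it shows only that more were sent. It could also hide the reverse, a lower opening rate in Enhanced.

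**Working it through.** The documents give no figure for texts sent or opened, so there is none to reproduce. The check uses the stated schedule.

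**Inputs**
- Period: the three-month intervention (Study Design).
- Enhanced: weekly, so 12 texts (4 per month) to 13 (52 weeks / 4).
- Basic: bi-monthly, undefined. Assumption A, twice a month: 6 texts. Assumption B, every two months: 1 to 2 texts.
- Common to both arms: one adherence text at the end of month one.
- Opening probability per text, *p*: not given; assumed equal in both arms.

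**Formula.** Expected opens = texts sent × *p*. With equal *p*, the ratio of expected opens is texts sent to Enhanced / texts sent to Basic; *p* cancels.

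**Results**

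| Reading | Enhanced v Basic texts | Ratio |
|---|---|---|
| A | 12 v 6 to 13 v 6 | 2.0 to 2.17 |
| A, with adherence text | 13 v 7 to 14 v 7 | 1.86 to 2.0 |
| B | 12 v 2 to 13 v 1 | 6 to 13 |
| B, with adherence text | 13 v 3 to 14 v 2 | 4.3 to 7 |

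Under A with 13 v 6 texts, *p* = 0.5 gives 13 × 0.5 = 6.5 opens against 6 × 0.5 = 3.0, and *p* = 0.9 gives 11.7 against 5.4.

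**Break-even.** A Basic woman who opens all 6 texts has the same count as an Enhanced woman who opens 6/13 = 46% of hers.

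**Messaging period.** Procedure Phase 3 also speaks of texts throughout the study. If both schedules ran for six months, both numbers would double (26 v 12) and the ratio would not change.

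**Appointment reminders.** Study Design and Figure 1 mention appointment reminders by text for Basic, with no number; Enhanced also receives reminders. If Basic alone received *a* extra texts, the ratio would be 13 / (6 + *a*), which reaches 1 only at *a* = 7. If both arms received *a* extra, it would be (13 + *a*) / (6 + *a*), which stays above 1.

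**Participant-level alternative.** The vendor wording could be read as the number of women who open at least one text. That measure also depends on volume: P(at least one) = 1 − (1 − *p*)^n. At an assumed *p* = 0.2 it is 1 − 0.8^13 = 94.5% with 13 texts and 1 − 0.8^6 = 73.8% with 6.

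**After the fix.** Opens / texts sent has expectation 13*p*/13 = *p* in Enhanced and 6*p*/6 = *p* in Basic, so the ratio is 1.0 when behaviour is the same.

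**The case against.** The strongest reply is that the count is a single clause in a design summary. The procedure section speaks of which participants opened texts, and the analysis paragraph says only that opened texts will be used. On that view the plan has an undefined measure rather than a settled choice of a biased one. Part of this stands: the wording is inconsistent, and participant-level weekly reports could support a fair rate. But no section defines that rate, the only explicit statement of what is compared is a number, and an at-least-one definition would not remove the problem. The attachment list includes one on outcomes and source that is not in the supplied text, so a definition there cannot be ruled out.

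It can also be said that the consequence is limited. That stands. The measure is neither a primary nor a secondary outcome, and no test is planned. The sentence on what will inform the full-scale intervention names participant quotes and poorly rated items, not text opens. A reader might infer a false-positive result or a biased efficacy conclusion; the documents support neither.

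Three other stronger readings should be set aside.
- A reader might infer an eight- or nine-fold artefact. That needs bi-monthly to mean every two months, which is the less natural reading for reminders to collect medication supplied in weekly packets.
- A reader might infer that re-sends inflate the count of opens, because the vendor "will also resend text messages if they remain unopened for more than two days". A text is re-sent only while unopened, and nothing says that opening two copies would count twice. Re-sends matter mainly for defining the denominator.
- A reader might infer that the vendor already logs sends for each woman. The protocol mentions data on opens only.

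**Conclusion.** The concern holds as a defect in a descriptive feasibility measure. Compared as worded, the number of texts opened would be about twice as high in Enhanced with no difference in behaviour. This rests on equal opening probability in the two arms, on bi-monthly meaning twice a month, and on appointment reminders not adding many more texts in Basic than in Enhanced. Reading bi-monthly as every two months makes the gap larger; a substantial number of Basic-only appointment reminders would make it smaller. The direction is the same under either reading of bi-monthly.

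It deserves correction despite its limited reach, because opened texts are one of only two objective feasibility measures and a better measure is available from nearly the same data.

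**What to change.** 1. In Study Design, and in the acceptability and feasibility paragraph of both the Analysis Plan and the SAP, replace the count with a per-woman proportion: distinct scheduled messages opened, divided by distinct scheduled messages sent to her. Treat a re-send as the same message in both numerator and denominator.
2. Summarise the proportion by arm with a 95% interval, in line with the plan's general rule for estimates. No test needs to be added.
3. Reword the vendor-data description in Procedure Phase 3 so that it yields this measure, and say whether the adherence text and appointment reminders count as scheduled messages.
4. State the existing Basic text frequency as a number per month.

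The cost is a few sentences, plus confirmation that the vendor's report or the sending schedule gives the number of messages sent to each woman. The intervention does not change. The proportion removes the effect of sending volume on the count; it will still reflect any real effect of message content or frequency on opening, which is what the pilot wants to see.

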Prevention Point Philadelphia (PPP). PPP is the only syringe exchange in Philadelphia. They promote health, empowerment and safety for communities affected by drug use and poverty by offering case management, syringe exchange, medical services, HIV and Hepatitis C (HCV) testing, addiction services, housing services, free meals, legal clinic and overdoes prevention and reversal training. PPP serves hundreds of people throughout the week, many of whom attend almost daily.

Sampling

Subjects will be screened for their interest in and eligibility for participating. We aim to enroll 68 women, assuming a 75% retention rate at the end of the intervention, leaving us a final study sample of 50. Treatment allocation will be accomplished using randomization through REDCap, a HIPAA approved research management software.

PROCEDURE PHASE 3

For graphic representation of study Procedure, see attached. Participants will be asked to participate after or while waiting for services at the study site. If they are interested, research staff will take participants into a designated private room and ask eligibility questions and be HIPAA consented. If they report that they meet the eligibility requirements, they will be taken to an HIV tester at Prevention Point Philadelphia for confirmation of status. If a woman tests positive for HIV, she will be provided regular counseling through PPP's testing program and given access to resources and services to link her to immediate care. If the woman does not have HIV and is eligible to be in the study, she will be consented into the study.

Once confirmed to be HIV-, participants will be randomized to a group using REDCap's randomization tool and a baseline survey will be conducted by research staff. All survey assessments will be orally administered to participants to address any literacy or cognitive issues. Responses will be entered into REDCap by a research staff member.

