After the baseline survey is complete, research staff will introduce the participant to the appropriate PrEP counselor. Individuals in the "Basic" group will be introduced to the current PrEP counselors at Prevention Point. Those in the "Enhanced" group will be introduced to a study counselor that will be providing the targeted messages and counseling. Initial counseling will be about PrEP and importance of adherence. The PrEP counselors will also make an appointment for the participant to meet with a doctor at Prevention Point to be assessed for whether PrEP is appropriate for the participant to take.

When the participant meets with the doctor at Prevention Point, they will use the Centers for Disease Control's diagnostic criteria for PrEP prescription (see Table 1). The doctor will not know whether the participant is in the control or intervention group. Once a participant has met with a doctor, completed testing, and is determined to be a good candidate for PrEP, their prescription will be sent to a participating pharmacy that provides medications to Prevention Point Philadelphia through their 340B clinic. 340B is a federal drug pricing program that Prevention Point Philadelphia is a member of.

Table 1. CDC Diagnostic Criteria for Prescribing PrEP

Physician will Provide at First Visit:	Physician will Provide at all visits
Assessment of possible Acute HIV infection	Assessment of HIV status
Lab screenings to determine indications (gonorrhea/chlamydia, P23+ HIV ½, RPR, HCV antibody with reflex to HCV viral load, HBV antigen and antibody, BMP for creatinine)	Assessment of side effects and advice on management

HIV risk assessment to determine PrEP indication	Assessment of adherence and counseling to support it
Medication fact sheet to patients with dosing, side effects	Assessment of STI symptoms, HIV risk behavior, counseling for risk reduction
Counseling on HIV risk reduction methods	Information on anything new regarding PrEP and respond to questions
Advice on adherence	
Advice on PrEP use with contraception and pregnancy	
Prescription for Truvada (a brand name of PrEP)	

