All participants will give informed consent to participate in the project and HIPAA consent to have access to health-related information. They will sign a PPP HIPAA consent that allows Project PEACE study staff to have access to their HIV test result, adherence information, and other medical information pertinent to the study. The research staff will read, review, and discuss consent forms with all potential participants prior to asking them to acknowledge the consent. If the potential participant appears confused or indicates she does not understand the consent, the moderator will attempt to identify the misunderstanding and to explain the consent again. If the potential participant still does not comprehend the consent, she will be excluded from the study. We will confirm that potential participants understand the material covered in the consent procedure by asking questions prior to asking the person to sign the consent form. These will include open-ended (e.g., "Could you tell me what's going to happen if you enroll in the study?") and closed questions (e.g., Will you get free medications as part of this research study?"). Responses that suggest confusion or inaccuracies that staff cannot successfully clarify will result in exclusion from the study and direction to appropriate outside referrals. If the participant agrees to participate, we will indicate this willingness on the REDcap project on a wireless tablet. We will provide a paper copy of the consents to the participant to take with her.

Provisions to Maintain the Confidentiality of Data

Assessment responses and all other data (e.g. % prescription pickups) will be entered into REDCap, which is protected behind Temple's firewall and HIPAA compliant. Each participant will be auto-populated with a study ID and no identifying information will be linked to the study record. Only the research staff will have access to, or be able to open, the REDCap database.

Risk to Participants

1. **PrEP use** - There are some risks to taking PrEP, including nausea, dizziness, headache and fatigue. These usually subside after a few weeks of taking the medication. The physician will assess each participant for appropriateness of taking PrEP and anyone who has counter indications will not be prescribed PrEP. They will also be monitored throughout the intervention by the medical staff at PPP to ensure that no one whose side effects may be damaging continues to take PrEP.

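### The procedure names randomisation before the interviewer-read baseline survey, and no visible text withholds the arm until the survey is saved, so secondary-outcome baselines may be collected with the arm known

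*Combined protocol and SAP*

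**What the plan says.** The relevant text is in the Procedure Phase 3 section. Once a woman is confirmed HIV-negative, "participants will be randomized to a group using REDCap's randomization tool and a baseline survey will be conducted by research staff". On how the survey is taken: "All survey assessments will be orally administered to participants to address any literacy or cognitive issues", and "Responses will be entered into REDCap by a research staff member". The next step is: "After the baseline survey is complete, research staff will introduce the participant to the appropriate PrEP counselor". The counselor differs by arm, so staff know the allocation by that point.

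The one masking statement concerns the prescriber: "The doctor will not know whether the participant is in the control or intervention group". Under Provisions to Maintain the Confidentiality of Data, the protocol adds: "Only the research staff will have access to, or be able to open, the REDCap database". The same system performs the randomisation. The SAP mentions neither allocation concealment nor masking of interviewers.

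The procedure section also points to material that is not in the supplied text: "For graphic representation of study Procedure, see attached".

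The Secondary outcomes paragraph of the SAP enters the baseline value of each outcome as a covariate in the linear models. It also measures perceptual-map movement in PrEP attitudes from baseline to month three and to the three-month follow-up. The Study Design section describes the secondary comparison as one of changes.

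**The concern.** Self-efficacy, decisional conflict and PrEP attitudes are subjective scales taken by interview. If the interviewer or the woman knows the arm while the baseline is being taken, the answers or their recording may differ between arms for reasons unrelated to pre-existing differences. Such a shift would enter the baseline-adjusted models through the covariate and the map comparison through its starting point.

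The SAP treats greater movement in the Enhanced arm as a sign of promise of efficacy, so this reading could be distorted. The adherence comparisons, which are primary, use no baseline score and are not at stake.

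A second, smaller matter is completeness. If randomisation comes first, a woman can be randomised without ever giving a baseline, and each such woman is 1/68 = 1.5% of the planned sample. The documents give no rate for this.

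**Working it through.** **Order of steps.** The text was read for anything that fixes the order or hides the arm.

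- The procedure sentence names randomisation first and the survey second, joined by a plain conjunction. HIV confirmation precedes both. No visible text gives the opposite order.
- Introduction to the counselor follows the survey, so the arm must be known by then. That fits either order.
- Counselor contact starts only after the survey. The possible problem is therefore knowledge of the arm, not exposure to the intervention.
- The statements limiting staff to de-identified data, under Risk to Participants and Privacy, concern confidentiality and do not hide the arm.

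**Size, as illustration.** The plan has no figure of its own on this point to reproduce.

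Inputs from the plan: 25 per arm projected for analysis, 68 randomised (34 per arm if equally split and none are lost), and significance at 0.05, taken as two-sided because sidedness is not stated.

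Assumed inputs: a shift of 0.1-0.3 SD in one arm, and a baseline-outcome correlation r of 0.5, with 0.3-0.7 as the range.

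Let b be the arm-related shift at baseline and f the shift at follow-up, both in SD. With equal SDs at the two times, the covariate slope is r, so:

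- bias of the adjusted difference = f − r·b
- bias of change or movement = f − b
- SE of the adjusted difference = √[(2/n)(1 − r²)], with 2n − 3 degrees of freedom

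At n = 25 and r = 0.5, SE = √(0.08 × 0.75) = 0.245 and the 95% CI half-width is 0.493 SD. Type I error comes from the non-central t distribution.

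| Scenario (n = 25, r = 0.5, d = 0.1-0.3) | Adjusted bias (SD) | Type I error | Bias in change or movement (SD) |
|---|---|---|---|
| A. Shift at baseline only (b = d, f = 0) | −0.05 to −0.15 | 5.5-9.2% | −0.1 to −0.3 |
| B. Same shift at both times, arm known at baseline (b = f = d) | +0.05 to +0.15 | 5.5-9.2% | 0 |
| C. Baseline taken before allocation, follow-up shift remains (b = 0, f = d) | +0.1 to +0.3 | 6.9-22.4% | +0.1 to +0.3 |

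The type I error column applies to the adjusted models only, because the SAP states no test for map movement.

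In scenario A the bias is 0.05/0.493 = 10% to 0.15/0.493 = 30% of the half-width, and it runs against the arm whose baseline was shifted favourably. With 34 per arm the half-width is 0.419 SD and type I error 5.6-10.8%. At 25 per arm, r from 0.3 to 0.7 gives a bias of 0.03-0.21 SD in magnitude and type I error of 5.1-17.5%.

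Comparing B with C shows the limit of reordering alone. If the same shift also occurs at follow-up, the adjusted bias goes from (1 − r)d to d, and the bias in change or movement from 0 to d.

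**The case against.** The strongest reply is that the documents do not establish that anyone knows the arm during the baseline survey. The conjunction does not order the two steps, and opening the sentence with HIV confirmation fits both equally. The attached graphic, and the timeline listed as Attachment A, may settle the order and cannot be seen here. The access statement is about confidentiality. It does not say who presses the randomisation button, who sees the allocation field, or that the interviewer and the randomiser are the same person. All of this stands, and it is why the point is worded as a possibility. What remains is that the sentence names randomisation first and no visible text supplies a safeguard.

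A second reply is that a baseline-only shift is the less natural scenario. Follow-up surveys are also oral, carry no stated masking, and are scheduled "at a time when they are already at Prevention Point and ideally meeting with their PrEP counselor" or there for other services. If knowledge of the arm moves answers at baseline, nothing suggests that it would stop doing so later. Scenarios B and C then show that reordering alone could leave a larger net bias. That also stands. It is a reason to say separately whether follow-up interviewers know the arm. It does not justify relying on an unprotected baseline, because full cancellation in change or movement needs equal shifts at both times, and even equal shifts leave (1 − r)d in the adjusted models.

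A third reply is that this is a pilot seeking directional insight. That limits the severity, but the correction is small enough to be worth making.

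**Conclusion.** The point holds as a minor one. As worded, the protocol leaves open that the baselines for the three secondary outcomes are collected with the arm known, and the visible text contains nothing to prevent it.

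Three stronger conclusions are tempting and are not supported:

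- **That the secondary baselines are biased, or that the trial's type I error is inflated by a given amount.** The documents give no shift, direction or correlation. The 0.05-0.15 SD bias and the 5.5-9.2% error rate follow only from the assumed values, and with no shift there is no bias.
- **That the intervention contaminates the baseline or affects the primary result.** Counselor contact follows the survey, and the adherence comparisons use no baseline score.
- **That reordering by itself reduces net bias.** It secures a clean starting value, but if the same shift d persists at follow-up, bias rises from (1 − r)d to d in the adjusted models and from 0 to d for change or movement.

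**What to change.** In the Procedure Phase 3 section, state the sequence outright: consent and HIV confirmation; baseline survey completed and saved in REDCap; REDCap randomisation; introduction to the counselor. If the attached graphic already shows this order, correct the sentence to match it.

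The gain is a pre-allocation baseline for every randomised woman. The cost is a small workflow edit in the protocol and REDCap and possibly a minor IRB amendment, with no added assessment.

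The downside is that any offset between a baseline shift and a similar follow-up shift is lost. A separate sentence should therefore say whether follow-up interviewers know the arm.
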